### 10.3 Procedures to Assess Efficacy (Biopsy and Disease Assessment)

#### 10.3.1 Radiologic Assessments

Computed tomography (with contrast) or MRI of chest, abdomen, and pelvis must be obtained within 28 days prior to the first IP dose. The same method (CT with contrast or MRI) must be used throughout the study. Subjects with brain metastasis should have MRI scans of the brain.

Radiographic assessment (and physical assessments of malignancy) should be performed at every 2 cycles starting at C3 (ie, C5, C7, C9, etc). Assessments must be performed prior to commencing treatment for that cycle. Post C9 assessment, subjects who have been determined to have obtained a clinical benefit from OP-1250 may reduce frequency of assessments to every 3 cycles (ie, C12, C15, C18, etc.) prior to commencing treatment for that cycle.

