**Subjects with Nontarget Lesions Only**

Non-Target Lesions	New Lesions	Overall Response
CR	No	CR
Non-CR / Non-PD	No	Non-CR / Non-PD
Not all evaluated	No	NE
Unequivocal PD	Yes or No	PD
Any	Yes	PD

Source: Eisenhauer EA, Therasse P, Bogaerts J, Schwartz LH, Sargent D, Ford R, et al. New response evaluation criteria in solid tumours: revised RECIST guideline (version 1.1). Eur J Cancer 2009;45(2):228-47.

Key: CR = complete response; NE = inevaluable; PD = progressive disease.

Any subject with a CR or PR is to have repeat assessments performed at 4 weeks later to confirm the response.

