10.1 Efficacy Endpoints

ORR

ORR is the primary efficacy endpoint in phase II (without cohort C) and secondary endpoint in phase I. Objective response will be determined using RECIST version 1.1. The overall tumor response at each time point will be recorded. A subject's best overall response will be derived as the best response over all time points, where responses from best to worst are CR, PR, SD, progressive disease (PD), and not evaluable (NE). Time point responses after the first assessment of PD will not be used in the derivation of confirmed best objective response. A confirmed response requires a CR or PR to be confirmed at a subsequent tumor assessment at least 4 weeks (28 days) from the initial assessment of CR or PR, and a confirmed response of SD requires the interval from first dose date to SD to be at least 6 weeks (42 days). To determine the best overall confirmed response in the presence of at least one time point response of CR or PR, the best response for each pair of assessments will be derived based on Table 2. The best overall confirmed response will then be the best over all of the pair best responses.

Table 2: Derivation of Best Overall Response when confirmation of CR and PR required

Overall response for 1 st time point	Overall response for subsequent time point	Best overall response for pair of assessments
CR	CR	CR if time requirement is met, otherwise NE
CR	PR	SD or PD or PR ^a
CR	SD	SD provided minimum criteria for SD duration met, otherwise, PD
CR	PD	SD provided minimum criteria for SD duration met, otherwise, PD
CR	NE	SD provided minimum criteria for SD duration met, otherwise NE
PR	CR	PR

PR	PR	PR
PR	SD	SD
PR	PD	SD provided minimum criteria for SD duration met, otherwise, PD
PR	NE	SD provided minimum criteria for SD duration met, otherwise, NE
NE	NE	NE

CR=complete response; PR=partial response; SD=stable disease; PD=progressive disease; NE=not evaluable.

^a : If a CR is truly met at first time point, then any disease seen at a subsequent time point, even disease meeting PR criteria relative to baseline, makes the disease PD at that point (since disease must have reappeared after CR). Best response would depend on whether minimum duration for SD was met. However, sometimes 'CR' may be claimed when subsequent scans suggest small lesions were likely still present and in fact the patient had PR, not CR at the first time point. Under these circumstances, the original CR should be changed to PR and the best response is PR.

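### SAP Table 2 sets the 28-day confirmation interval for CR-CR only, so a confirmatory scan done too early can be scored against the SAP's own text

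*SAP*

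**What the plan says.** SAP Section 10.1 treats a response of either kind as established only when it is "confirmed at a subsequent tumor assessment at least 4 weeks (28 days) from the initial assessment of CR or PR". It then says that "the best response for each pair of assessments will be derived based on Table 2", and that "The best overall confirmed response will then be the best over all of the pair best responses". The confirmed ORR counts only subjects whose best overall response is a confirmed CR or PR.

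In Table 2 the CR-CR row reads "CR if time requirement is met, otherwise NE". The PR-PR and PR-CR rows give PR, with no time condition. The CR-NE row reads "SD provided minimum criteria for SD duration met, otherwise NE". CR-SD and CR-PD also give SD once the SD minimum is met, and PD if it is not. The SD minimum is 42 days from first dose, and the SAP ranks NE lowest of the five categories.

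The closing note of protocol Appendix E states: "Any subject with a CR or PR is to have repeat assessments performed at 4 weeks later to confirm the response". It gives no minimum interval and no window. Protocol Section 10.3.1 and Table 1 footnote 17 place imaging every two 28-day cycles, with every three cycles allowed after C9 for subjects with clinical benefit. Neither lists a four-week repeat.

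**The concern.** Table 2 is the operative rule for best overall response, which feeds the Phase II primary efficacy endpoint. It disagrees with the paragraph above it on when a PR is confirmed. Two programmers could each follow the SAP faithfully and produce different responder lists.

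The CR-CR row has a separate fault. Two complete responses too close together are scored lower than one complete response followed by progression or by a scan that could not be evaluated.

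The trial is single-arm, open-label and investigator-assessed, so the responder rule should leave no choice to be made after the data are seen.

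**Working it through.** No stated figure is in dispute. For context, the SAP's precision of ±15% for 50 subjects reproduces: the largest distance from estimate to exact (Clopper-Pearson) 95% limit, over all possible counts, is 14.8 points.

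**1. Text against table.** For a gap between the two assessments of:

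| Pair | Text, under 28 days | Table 2, under 28 days | Text and Table 2, 28 days or more |
|---|---|---|---|
| CR-CR | not confirmed | NE | CR |
| PR-PR | not confirmed | PR | PR |
| PR-CR | not confirmed | PR | PR |

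At 28 days or more the two sources agree on all three rows. Below 28 days they disagree on whether PR-PR and PR-CR make a responder. For CR-CR they agree that the response is unconfirmed; only the fallback category is at issue.

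**2. The CR-CR fallback.** The first scheduled scan, at C3 Day 1, falls 2 × 28 = 56 days after first dose. With the ±5-day window that Table 1 appears to give this visit, that is 51 to 61 days, past the 42-day SD minimum. From then on, CR-SD, CR-PD and CR-NE all give SD, while CR-CR at 27 days gives NE.

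**3. When a gap under 28 days can occur.**
- Scheduled scans are 2 × 28 = 56 days apart. With opposed ±5-day windows the minimum is 56 − 10 = 46 days, so a scheduled pair always qualifies.
- The Appendix E repeat, done exactly on time, is at 28 days and qualifies.
- No window is stated for that repeat. If ±5 days applied to both scans (an assumption), the gap could be 28 − 10 = 18 to 28 + 10 = 38 days.

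**4. Rescue by later scans.** The best of all pairs is taken. A response still present at the next scheduled scan, nominally 56 days after it was first seen, is confirmed whatever happened at the early repeat. The misclassification lasts only if no later pair qualifies: progression comes next, the next scan is missing, or data cutoff intervenes.

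**5. Effect on ORR.** One subject is 1/50 = 2 points. With assumed counts, 10/50 = 20% (exact 95% CI 10.0 to 33.7), and 11/50 = 22% (11.5 to 36.0) if one short-interval PR pair is counted.

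**6. Effect on CBR.** Take a hypothetical subject with SD at C3 and C5, a first CR at C7 Day 1 (6 × 28 = 168 days after first dose), a repeat CR 25 days later, then data cutoff. Time on treatment is 168 + 25 = 193 days, above the 24 weeks (168 days) required. Table 2 has no row beginning with SD, so read literally the only pair it scores is CR-CR, which gives NE. The subject is outside the CBR numerator. If the earlier SD time points were also carried into the derivation, the subject would be SD and would count; the SAP does not say that they are.

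**The case against.** The strongest reply is that the 28-day rule for PR is already fixed. The paragraph before Table 2 states it for both CR and PR, the table's title says it applies where confirmation is required, and the endpoint counts only confirmed responses. On this view the short PR rows are an omission that no careful programmer would act on. That stands in part: the intent is clear, and a reader should not infer that the SAP has settled that short-interval PRs count. It does not remove the problem. The text sends each pair to the table and gives no fallback category for a PR pair that is too close, so its result (SD or NE) is undefined even for someone who follows the text.

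Three stronger readings are tempting, and the documents do not support them:
- **Short-interval repeats will be common.** A reader might borrow the ±5-day visit window, assume uniform timing and compute a share. No window is given for the repeat, nothing ties it to a clinic visit, and Table 1 shows no imaging in even cycles.
- **The NE result lowers ORR.** NE and SD are both non-response.
- **Any subject with two close CRs loses clinical benefit.** Someone whose follow-up ends after an early repeat, for example near day 80, cannot reach 24 weeks on treatment and is outside the CBR numerator under any wording of Table 2. Only a late responder, as in step 6, can be affected.

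**Conclusion.** The inconsistency is real and should be corrected before database lock, but its reach is narrow. Table 2 conflicts with the SAP text on short-interval PR-PR and PR-CR pairs, and its CR-CR fallback ranks two close CRs below a CR followed by progression.

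An ORR discrepancy requires three things together: the table is programmed literally, the Appendix E repeat falls under 28 days after the response, and no later pair qualifies. Its size is 2 points per affected subject, assuming a denominator of 50. The number affected cannot be derived from the documents and may be zero. The CR-CR fault leaves ORR unchanged; it affects the best overall response table and, for a late responder, possibly CBR.

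**What to change.** In SAP Table 2, change three rows:
- CR-CR: *CR if the assessments are at least 28 days apart; if not, SD when the 42-day minimum from first dose has been reached; failing that, NE.*
- PR-PR and PR-CR: *PR if the assessments are at least 28 days apart, with the same SD-then-NE fallback.*

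In protocol Appendix E, make the repeat due *at least 4 weeks (28 days)* after the response. Then reconcile that repeat with Table 1 footnote 17 and Section 10.3.1, so that sites see one imaging schedule. Appendix E requires the repeat, so whether it stays as a separate scan is for the sponsor to decide and state; aligning the interval does not settle that.

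The cost is three table rows, one protocol sentence and a schedule cross-reference. No result at 28 days or more changes, and the row edits need no extra scan. The downside is that a PR repeated in under 28 days, with no later confirming scan, will not count as confirmed.

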### STUDY ENDPOINTS:

The study objectives and endpoints of each of the 2 parts of the study are:

Phase I (Part A [Dose Escalation] and Part B [Dose Expansion])	
Primary Objectives	Primary Endpoints

 
To identify the MTD and/or RP2D of OP-1250 (Part A [Dose Escalation]).
 
	
 
Incidence and nature of DLTs as defined Section 8.8.2.
 
MTD and/or RP2D of OP-1250 when used as a single agent.
 

 
To confirm the RP2D of OP-1250 (Part B [Dose Expansion]).
 
	
 
RP2D of OP-1250 when used as a single agent.
 

 
To assess the safety and tolerability of OP-1250 (Parts A [Dose Escalation] and B [Dose Expansion]).
 
	
 
Incidence, nature, and severity of TEAEs and SAEs according to NCI-CTCAE version 5.0.
 

 
To assess the PK of OP-1250 (Parts A [Dose Escalation] and B [Dose Expansion]).
 
	
 
Plasma levels of OP-1250 at pre-defined intervals to establish PK parameters (including: Cmax, Cmin, Tmax, AUC, t1/2, and OP-1250 trough concentration at steady state).
 

Secondary Objectives	Secondary Endpoints

 
To estimate the ORR defined as the CR + PR rate of OP-1250.
 
	
 
ORR by evaluation of tumor response assessments using RECIST 1.1 in subjects with measurable disease.
 

 
To estimate the CBR (CR + PR + SD ≥ 24 weeks) of OP-1250.
 
	
 
CBR, as defined by percent of subjects with CR + PR + SD ≥ 24 weeks, by evaluation of tumor response assessments using RECIST 1.1.
 

 
[REDACTED]
 
	
 
[REDACTED]
 

Exploratory Objectives	Exploratory Endpoints

 
[REDACTED]
 
	
 
[REDACTED]
 

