### 10.5.3 End of Treatment

The EOT visit should occur within 42 days after administration of the last dose of IP.

For any subject who has been withdrawn from the study (see [Section 8.3.3](#)), the tests and evaluations listed for the EOT visit should be performed, if possible. The assessments to be performed at the EOT visit are detailed in the Schedule of Events in [Table 1](#).

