3. STUDY ENDPOINTS

The study endpoints of each of the 2 phases of the study are:

Phase I (Dose Escalation and Expansion)

Primary Endpoints:

- Incidence and nature of DLTs as defined in the protocol.
- MTD and/or RP2D of OP-1250 when used as a single agent.
- Incidence, nature, and severity of treatment-emergent Adverse Events (TEAEs) and serious adverse events (SAEs) according to NCI-CTCAE version 5.0.
- Plasma levels of OP-1250 at pre-defined intervals to establish PK parameters (includes maximum concentration (C_{max}), minimum concentration (C_{min}), time to maximum concentration (T_{max}), area under the curve (AUC), half-life (t_{1/2}), and OP-1250 trough concentration at steady state).

Secondary Endpoints:

- ORR by evaluation of tumor response assessments using RECIST 1.1 in subjects with measurable disease.
- CBR as defined by percent of subjects with CR + PR + SD \geq 24 weeks, by evaluation of tumor response assessments using RECIST 1.1.

• [REDACTED]

[REDACTED]

- [REDACTED]
- [REDACTED]
- [REDACTED]
- [REDACTED]
- [REDACTED]
- [REDACTED]

Phase II

Primary Endpoints:

- ORR by evaluation of tumor response assessments using RECIST 1.1 in subjects without evidence of CNS metastases who have measurable disease.
- Incidence, nature, and severity of TEAEs and SAEs according to National Cancer Institute-Common Terminology Criteria for Adverse Events (NCI-CTCAE) version 5.0.
- Plasma levels of OP-1250 at pre-defined intervals to establish PK parameters (includes C_{max}, C_{min}, T_{max}, AUC, t_{1/2}, and OP-1250 trough concentration at steady state). The results of those analyses will be reported separately in PK report.

Secondary Endpoints:

- CBR as defined by percent of subjects with a CR + PR + SD for ≥ 24 weeks, by evaluation of tumor response assessments using RECIST 1.1 in subjects without evidence of CNS metastases.

█

████████████████████

█

█

█

█

█

█

█

█

█

█

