The confirmed ORR is defined as the proportion of subjects with a best overall response of confirmed CR or PR in EFS with measurable disease at baseline.

The secondary efficacy endpoints for Phase II are:

CBR

CBR is defined as the proportion of subjects with a confirmed CR, PR, or SD and who had been on treatment for ≥ 24 weeks. Subjects who had disease progression per RECIST 1.1 7 days before Cycle 7 day 1 will not be considered as clinical benefit. Duration of treatment is defined as time from the first dose date of study treatment to end of treatment date for subjects discontinued treatment or to data cutoff date for ongoing subjects.

CBR will be summarized based on CBR Analysis Set (without cohort C) defined in 8.6.

[REDACTED]

[REDACTED]

[REDACTED]

[REDACTED]	[REDACTED]	[REDACTED]
------------	------------	------------

[REDACTED]	[REDACTED]	[REDACTED]
[REDACTED]	[REDACTED]	[REDACTED]
[REDACTED]	[REDACTED]	[REDACTED]
[REDACTED]	[REDACTED]	[REDACTED]

[REDACTED]

[REDACTED]

[REDACTED]

[REDACTED]

[REDACTED]	[REDACTED]	[REDACTED]
[REDACTED]	[REDACTED]	[REDACTED]
[REDACTED]	[REDACTED]	[REDACTED]
[REDACTED]	[REDACTED]	[REDACTED]

[REDACTED]	[REDACTED]	[REDACTED]
[REDACTED]	[REDACTED]	[REDACTED]
[REDACTED]	[REDACTED]	[REDACTED]

[REDACTED]

[REDACTED]

[REDACTED]

[REDACTED]

[REDACTED]	[REDACTED]	[REDACTED]
[REDACTED]	[REDACTED]	[REDACTED]
[REDACTED]	[REDACTED]	[REDACTED]
[REDACTED]	[REDACTED]	[REDACTED]
[REDACTED]	[REDACTED]	[REDACTED]
[REDACTED]	[REDACTED]	[REDACTED]

[REDACTED]	[REDACTED]	[REDACTED]
------------	------------	------------

[REDACTED]

[REDACTED]

[REDACTED]

[REDACTED]

[REDACTED]

[REDACTED]

[REDACTED]

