13.3 Extent of Exposure

The analysis will be conducted using SAF set.

Study drug exposure will be summarized using the total number of doses received, total number of cycles, duration of study treatment, relative dose intensity, number of dose interruption, and number of dose reduction. Duration of treatment in weeks is defined as the (last dose date - the first dose date + 1)/7. Relative dose intensity will be calculated as the total amount of dose received divided by (the duration on treatment (in days) × assigned dose). The number of subjects with dose interruption, dose reduction and the reason of dose interruption, dose reduction, the number of dose interruptions and dose reductions will be summarized by frequencies and percentages.

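### SAP 10.1 does not implement the protocol's clinical benefit rate: the 24-week test moves from stable disease to time on treatment, and the progression cut-off is ambiguous

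*SAP*

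**What the plan says.** - **Protocol, Synopsis endpoints and Table 5.** Phase I CBR is the "percent of subjects with CR + PR + SD ≥ 24 weeks, by evaluation of tumor response assessments using RECIST 1.1". Phase II uses the same form for subjects without CNS metastases.
- **SAP section 3.** The Phase II endpoint agrees: "percent of subjects with a CR + PR + SD for ≥ 24 weeks, by evaluation of tumor response assessments".
- **SAP 10.1, CBR.** The operational definition differs: "proportion of subjects with a confirmed CR, PR, or SD and who had been on treatment for ≥ 24 weeks". The same section lets SD count as confirmed once it is seen at least 42 days after first dose.
- **SAP 10.1, progression rule.** "Subjects who had disease progression per RECIST 1.1 7 days before Cycle 7 day 1 will not be considered as clinical benefit".
- **SAP 10.1, treatment duration for CBR.** It runs from first dose to an end-of-treatment date that is not defined, or to data cutoff for ongoing subjects. SAP 13.3 is explicit for exposure: "Duration of treatment in weeks is defined as the (last dose date - the first dose date + 1)/7". Protocol 10.5.3 adds: "The EOT visit should occur within 42 days after administration of the last dose of IP".
- **SAP 8.6, CBR analysis set.** Subjects with under 24 weeks on treatment and no radiographic progression are left out.
- **Protocol 10.3.1.** Scans fall at Cycles 3, 5, 7 and 9, and "Assessments must be performed prior to commencing treatment for that cycle".

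**The concern.** In the protocol, the 24 weeks qualify stable disease as shown by scans. In SAP 10.1 they qualify time on drug, and they apply to CR and PR as well as to SD. The disease-control element that remains for a stable subject is a six-week SD plus the progression sentence, and that sentence can be programmed in two opposite ways. Under one reading, a subject whose own week-24 scan shows progression can be reported as having clinical benefit.

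CBR is a named Phase II secondary endpoint. Clinical benefit is also given as an example of the anti-tumor activity weighed in the review that gates Phase II and in the end-of-Phase-II risk:benefit review (Protocol 11.4.2 and 11.4.3).

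**Working it through.** **1. The plan's own figure.** The only figure the documents attach to clinical benefit is precision: ±19% at n = 30 and ±15% at n = 50 (SAP 5.2, 5.3). Exact Clopper-Pearson 95% limits at a 50% rate give:
- 15/30: 31.3% to 68.7%, half-width 18.7 points.
- 25/50: 35.5% to 64.5%, half-width 14.5 points. The largest distance from estimate to limit over all counts at n = 50 is 14.8 points.

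Both stated figures reproduce. No CBR is assumed anywhere, so nothing else can be reproduced.

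**2. Calendar (28-day cycles).**
- C5D1 = 4 × 28 + 1 = Day 113 (week 16).
- C7D1 = 6 × 28 + 1 = Day 169 (24 weeks completed).
- Cut-off = 169 − 7 = Day 162.
- The C7D1 visit window appears to be ±5 days (Protocol Table 1), which is Days 164 to 174. A scan taken early in that window, before dosing, falls after the cut-off.
- A last dose on Day 168 gives 168 − 1 + 1 = 168 days = 24.0 weeks.

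**3. Classification by date of first PD.** Assume SD at the earlier scans and a treatment duration of at least 24 weeks.

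| First PD | Reading A: PD on or before Day 162 disqualifies | Reading B: PD within the 7 days before C7D1 disqualifies | Protocol: SD of at least 24 weeks |
|---|---|---|---|
| Before Day 162 | Not benefit | Not excluded by this sentence | Not met |
| Day 162 | Not benefit | Not benefit | Not met |
| Days 163–167 | **Benefit** | Not benefit | Not met on any count |
| Day 168 | Benefit | Not benefit | Depends on convention |
| Day 169 | Benefit | Benefit | Depends on convention |

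The last two rows are open because the protocol does not say how SD duration is measured. If SD runs from first dose to PD, PD on Day 169 follows 168 days, or 24.0 weeks. If SD must be shown by a scan at about week 24, the last scheduled SD scan is at week 16 and the condition fails.

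**4. Confirmed responders who stop before week 24.** The protocol counts them. Under the SAP, those with PD stay in the denominator as failures (10.1), and those without PD leave the denominator (8.6). Neither group is counted as benefit. Dropping a responder lowers CBR; dropping a non-responder without PD raises it.

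**5. End-of-treatment date.** If it is the last dose, 24 weeks means dosing to Day 168. If it were the EOT visit, a last dose on Day 126 (18 weeks) plus 42 days reaches Day 168.

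**6. Size.** One subject in 50 is 2.0 points. For a ceiling, assume exponential progression-free survival, S(t) = 0.5^(t/median), with the medians of 2.8 and 6.9 months that Protocol 6.1 quotes from a cited trial of later-line therapy. These are not design inputs. Weeks = months × 30.4375/7.

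| Median | S(16 wk) | S(24 wk) | Difference | Subjects per 50 |
|---|---|---|---|---|
| 2.8 months (12.2 wk) | 40.2% | 25.5% | 14.7 points | about 7 |
| 6.9 months (30.0 wk) | 69.1% | 57.4% | 11.7 points | about 6 |

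The difference is the share progressing between the week-16 and week-24 scans. It equals the inflation only if Reading A applies, every such subject has the Cycle 7 scan after Day 162, and every one reaches 24 weeks on treatment.

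**The case against.** The other side has several good points.

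- **Disease control is not discarded.** A reader might infer that time on drug replaces it altogether. It does not: a confirmed CR, PR or SD of at least six weeks is still needed, and RECIST progression is a listed reason to end treatment (Protocol 8.11). Only the 24-week duration has moved.
- **Week-24 PD does not count automatically.** The subject must also reach 24 weeks on treatment. With duration measured to last dose, someone with PD on Day 165 who stops that day is a non-benefit. The protocol sets no limit on how early the Cycle 7 scan may be, and PD on a scan by Day 162 disqualifies under Reading A.
- **Seven days can be seen as visit tolerance.** The outright conflict covers only Days 163 to 167.
- **Reading B removes most of the inflation.** It disqualifies PD on Days 162 to 168. One might infer that it then lets all earlier progressors through, but those who stop for PD would generally fail the 24-week treatment test.
- **Early-stopping responders do not all fail.** SAP 8.6 removes those without PD rather than failing them.
- **The EOT-visit reading is not shown.** SAP 10.1 does not name the visit, and SAP 13.3 uses last dose. This is an undefined term, not a demonstrated error.
- **SAP 2.2 and section 3 keep the protocol definition.** The fault is therefore partly an inconsistency inside the SAP.

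These points narrow the concern and cut its likely size. They do not make SAP 10.1 equivalent to the protocol endpoint, and they do not settle which reading of the progression sentence is meant.

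**Conclusion.** SAP 10.1 does not implement the CBR defined in the protocol and in SAP section 3. It transfers the 24-week requirement from documented SD to treatment duration and extends it to CR and PR. Its progression rule has two readings. On one, PD first seen on Days 163 to 167 can be reported as benefit, which conflicts with the protocol however SD is counted. For PD dated Day 168 or 169, a conflict exists only if SD must be documented by a scan at about week 24.

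The documents do not support a claim that CBR will be inflated by 12 to 15 points. Those figures are ceilings under assumed exponential progression-free survival and the conditions in step 6, and they include the arguable Days 168 and 169. Losing early-stopping responders pulls the other way, so the net direction is unknown. What is certain is 2 points per misclassified subject at n = 50, against a planned precision of ±15%.

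This should be fixed before database lock. CBR is secondary and descriptive, and the primary ORR is unaffected.

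**What to change.** In SAP 10.1, define clinical benefit as either of:

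- confirmed CR or PR at any time; or
- SD with no RECIST PD up to and including the week-24 (Cycle 7) assessment, and a last non-PD assessment at least 24 weeks minus a stated visit window after first dose. With a 7-day window this is 168 − 7 = 161 days.

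The tolerance then applies to the non-PD scan, not to progression. In addition:

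- For subjects with non-target disease only, let Non-CR/Non-PD (Protocol Table 15) stand in for SD. Cohort B is part of the CBR analysis and cannot otherwise meet the SD branch.
- Anchor the rule to first-dose date rather than C7D1, and delete the treatment-duration criterion. The undefined end-of-treatment date then drops out of CBR.
- Revise SAP 8.6 so that subjects are not excluded for being on treatment under 24 weeks. Without this, a confirmed responder who stops early without PD is still lost and the numerator change has no effect for that subject.
- Align SAP 10.1 with SAP section 3 and the protocol.

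The cost is SAP wording and derivation code, with no new data. The downside is that the reported CBR may fall.
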